

• To compare the PK of GSK2798745 with the effect of prophylactic dosing on alveolar-septal barrier permeability following LPS challenge in healthy volunteers.

• To investigate the effect of GSK2798745 on white blood cell levels (except neutrophils) in LPS-challenged lungs.

	

• Comparison of PK parameters of GSK2798745 in plasma with baseline corrected total protein concentration in BAL.

• Baseline adjusted total and differential cell count of white blood cells (except neutrophils) in BAL samples at 24 h after segmental LPS challenge.

[figure not shown]

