2.2. Study Objective(s) and Endpoint(s)

Objectives	Endpoints
Primary Objectives	Primary Endpoints

 To investigate the effect of GSK2798745 on alveolar-septal barrier permeability following LPS challenge in healthy participants. 	
 Baseline adjusted total protein concentration in bronchoalveolar lavage (BAL) samples at 26 h (24 h after segmental LPS challenge).
Secondary Objectives	Secondary Endpoints

 To investigate the effect of GSK2798745 on neutrophil levels in LPS-challenged lungs. To assess the safety and tolerability of GSK2798745 in LPS-challenged, healthy participants. To assess the pharmacokinetics (PK) of GSK2798745 in plasma in LPS-challenged, healthy volunteers 	
 Baseline adjusted total and differential cell count of neutrophils in BAL samples at 26 h (24 h after segmental LPS challenge). Adverse events (AEs), laboratory safety assessments, 12-lead electrocardiogram (ECG), physical examination, vital signs, spirometry (forced expiratory volume in 1 second [FEV1] and forced vital capacity [FVC]), faecal occult blood test (FOBT). PK parameters of GSK2798745 in plasma (including AUC (0-26) and Cmax).
Exploratory Objectives	Exploratory Endpoints

 To assess concentration of GSK2798745 in BAL 	
 Levels of GSK2798745 in BAL samples at 2h and 26h after dosing

Objectives	Endpoints

To investigate the effect of GSK2798745 on exploratory markers of endothelial barrier permeability and/or injury, and inflammation, in LPS-challenged lungs.	
Baseline adjusted levels of exploratory biomarkers in blood and/or BAL.

To possibly assess metabolite GSK3526876 (major metabolite of GSK2798745) in plasma and BAL samples.	
Plasma and BAL concentrations of metabolite GSK3526876.

To compare the PK of GSK2798745 with the effect of prophylactic dosing on alveolar-septal barrier permeability following LPS challenge in healthy volunteers.	
Comparison of PK parameters of GSK2798745 in plasma and BAL with baseline corrected total protein concentration in BAL.

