10.1. Statistical Analyses / Methods

A summary of the planned pharmacokinetic / pharmacodynamic analyses are outlined below:

- Individual plasma GSK2798745 C_{max}, will be plotted against corresponding BAL 2h GSK2798745 drug levels. Analysis may be undertaken to assess relationship of drug levels in plasma and target site (BAL).
- Individual plasma GSK2798745 AUC(0-26) and C₂₆ data will be plotted against BAL 26h GSK2798745 drug levels. Regression analysis will be undertaken to assess relationship of drug levels in plasma and target site (BAL)
- Individual plasma GSK2798745 AUC(0-26), C₂₆ and C_{max} data will be plotted against total BAL protein at 26h (primary clinical endpoint). Placebo treatment data (i.e. 0 drug concentration and corresponding total BAL protein will also be included in the PK-PD analysis. Analysis may be undertaken to evaluate the association between GSK2798745 PK parameters and change in BAL total protein.

Data specifications for PK/PD analyses presented in [Appendix 11: Pharmacokinetic / Pharmacodynamic Analyses](#).

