12.9. Appendix 9: Pharmacokinetic / Pharmacodynamic Analyses

12.9.1. Pharmacokinetic / Pharmacodynamic Dataset Specification

Specification for PK-PD dataset [Proposed dataset name PKPD]

Variable short name	Assessment description	Format	Unit	Valid Values / Format
C	Data Identifier	Integer	-	0
ID	Unique subject number	Numeric		Different ID for different subject
STUD	Protocol Number	Integer	-	207464
SUBJ	Subject identifier in study	Integer	-	Maximum 10 characters (numeric or text). Different identifier for each subject
CENT	Study centre identifier	Integer	-	
DAY	Day of sampling	Integer	See footnotes	See footnotes
C2	Conc of GSK2798745 2 h post first dose	Decimal 3 d.p	ng/mL	Numeric – For placebo TRT arm C2 = 0
C26	Conc of GSK2798745 26 h post first dose	Decimal 3 d.p	ng/mL	Numeric - For placebo TRT arm C26 = 0
AUC26	Area under curve (0-26h)	Decimal 3 d.p	ng.h/mL	Numeric - For placebo TRT arm AUC26 = 0
Analyte	Drug analysed	Integer	-	GSK2798745
Base_PD	Baseline corrected BAL total protein (i.e. before LPS challenge and 2h post dose)	Decimal 3 d.p	-	BAL total protein
745_PD	Corrected BAL total protein at 26h post dosing with GSK2798745 (i.e. 24h post LPS challenge)	Decimal 3 d.p		BAL total protein
AGE	Age	Decimal	Yrs	Integer. Age in years at time of screening rounded down to give age at last birthday.
WT	Weight	Decimal	Kg	Weight in kilograms at time of screening.
BMI	Body mass index	Decimal	kg/m ²	Body mass index calculated as weight divided by height squared
SEX	Subject gender	Integer	-	Integer. One of the following - 1 = Male

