12.11.10. Pharmacokinetic / Pharmacodynamic Figures

Pharmacokinetic / Pharmacodynamic: Figures					
No.	Population	IDSL / Example Shell	Title	Programming Notes	Deliverable [Priority]
PK / PD					
7.1.	Evaluable	PKPD_F1	Scatter Plots of Plasma PK Parameters (AUC_{0-26} , C_{26} , C_{max}) v 26h BAL Total Protein.	Page 1: Plasma AUC_{0-26} v 26h BAL Total Protein Page 2: Plasma C_{26} v 26h BAL Total Protein Page 3: Plasma C_{MAX} v 26h BAL Total Protein	SAC [1]
7.2.	Evaluable	PKPD_F1	Plots of BAL GSK2798745 Concentrations v 26h BAL Total Protein	Page 1: BAL C_2 v 26h BAL Total Protein Page 2: BAL C_{26} v 26h BAL Total Protein	SAC [1]

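### The PK/PD endpoint is defined on baseline-corrected BAL protein, but the only committed PK/PD displays plot the uncorrected 26 h value, and the analysis of change is optional and undefined

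*SAP*

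**What the plan says.** **Endpoint.** Protocol section 4 lists, among the exploratory endpoints, "Comparison of PK parameters of GSK2798745 in plasma with baseline corrected total protein concentration in BAL". SAP 2.2 keeps the same response and adds BAL drug levels on the exposure side: "Comparison of PK parameters of GSK2798745 in plasma and BAL with baseline corrected total protein concentration in BAL".

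**Committed displays.** SAP 10.1 says that individual plasma AUC(0-26), C26 and Cmax "data will be plotted against total BAL protein at 26h (primary clinical endpoint", with placebo participants entered at zero exposure. SAP 12.11.10 lists two PK/PD figures. Figure 7.1 ("Scatter Plots of Plasma PK Parameters" against 26 h BAL total protein) has three pages. Figure 7.2 ("Plots of BAL GSK2798745 Concentrations v 26h BAL Total Protein") has two. Neither the titles nor the programming notes mention baseline.

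**Optional analysis.** The same bullet of SAP 10.1 ends: "Analysis may be undertaken to evaluate the association between GSK2798745 PK parameters and change in BAL total protein". It does not define change, name a model or point to a display.

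**Dataset.** SAP 12.9.1 (Appendix 9) describes Base_PD as "Baseline corrected BAL total protein (i.e. before LPS challenge and 2h post dose" and 745_PD as "Corrected BAL total protein at 26h post dosing with GSK2798745 (i.e. 24h post LPS challenge".

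**The concern.** The endpoint names a baseline-corrected response, and nothing the SAP firmly commits to in its PK/PD section uses one. The contrast within SAP 10.1 is telling: the comparison of plasma exposure with BAL drug level at 26 h is promised a regression, while the comparison with protein, which is the defined endpoint, is promised only plots of a different quantity.

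Exposure among treated participants is not randomised. Differences between people in their starting protein therefore add scatter to any exposure-response relation, and bias it where starting protein happens to go with exposure. The 2 h value that would deal with this is already collected. SAP 5.3.1 makes it the default covariate for BAL markers, and the primary model in SAP 7.1.5.1 uses it.

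The dataset labels add a practical risk. Base_PD is called baseline corrected but is described as the pre-challenge 2 h value, that is, the baseline itself. 745_PD is called corrected without saying for what; SAP 12.6.3 uses that word for urea dilution. It is also described only for dosing with GSK2798745, although SAP 10.1 includes placebo. Two programmers could reasonably build different datasets from this specification.

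**Working it through.** The point rests on comparing texts. It depends on no sample size, power or error rate, so there is no figure in the plan to reproduce.

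| Place | Response | Status |
|---|---|---|
| Protocol 4, SAP 2.2 | baseline-corrected protein | endpoint definition |
| SAP 10.1, plots | 26 h protein, uncorrected | committed |
| Figures 7.1 (3 pages), 7.2 (2 pages) | 26 h protein, uncorrected | committed |
| SAP 10.1, last sentence of the bullet | change in protein, not defined | optional, no display |
| SAP 12.9.1 | Base_PD and 745_PD | meaning of corrected unclear |

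The rows do not meet: no committed output carries the response in the definition.

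**Illustration of size.** The inputs are the example values for placebo in mock shell PD_T1 (SAP Appendix 12). These are placeholders, not trial data: baseline minimum 33.15, median 84.07, maximum 190.94 µg/mL; 26 h LPS-lobe median 245.46 µg/mL; log-scale SDs s_b = 0.29 (baseline) and s_26 = 0.48 (26 h). The correlation r between log 2 h and log 26 h protein is not in the documents, so it is varied.

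1. *Same height, different ratio to baseline.* At 245.46 µg/mL, the three baselines give 245.46/33.15 = 7.4, 245.46/84.07 = 2.9 and 245.46/190.94 = 1.3. This pairs the extremes deliberately and is a worst case.
2. *How far the raw value stands in for change.* The correlation of log 26 h with log(26 h/2 h) is (s_26 − r·s_b)/√(s_b² + s_26² − 2·r·s_b·s_26). It is 0.86 at r = 0, 0.80 at r = 0.5 and 0.87 at r = 0.9. The raw value loses information but still tracks change.
3. *Which correction helps.* SD of the log ratio = √(s_b² + s_26² − 2·r·s_b·s_26); residual SD after covariate adjustment = s_26·√(1 − r²).

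| r | raw log 26 h | log ratio | covariate-adjusted |
|---|---|---|---|
| 0 | 0.480 | 0.561 | 0.480 |
| 0.3 | 0.480 | 0.481 | 0.458 |
| 0.5 | 0.480 | 0.419 | 0.416 |
| 0.7 | 0.480 | 0.346 | 0.343 |

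The ratio beats the raw value only when r exceeds s_b/(2·s_26) = 0.29/0.96 = 0.30. Covariate adjustment is never worse, apart from one degree of freedom.

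4. *Gain for a regression.* Adjustment removes r² of the residual variance: 9% at r = 0.3 and 36% at r = 0.6. If exposure is unrelated to baseline, this equals 1/(1 − r²) − 1 = 10% to 56% more participants.

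**The case against.** **The plan does not model raw protein.** SAP 10.1 commits only to scatter plots of the 26 h value, and the one exposure-response analysis it names is on change. This stands. A reader might infer that the exposure-response analysis is run on raw protein, so that participants with very different LPS responses count as equal. The documents do not support that: no such regression is planned, and only participants who share a 26 h value are plotted alike.

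**The 26 h value is the primary endpoint.** SAP 10.1 calls it so and SAP 7.1.1 agrees, so plotting it is legitimate. That justifies keeping the raw plot. It does not supply the baseline-corrected comparison: in the primary analysis baseline enters through the model, and a scatter plot has no model.

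**The baseline is imperfect.** It comes from an unchallenged left lower lobe segment, while the 26 h value comes from the challenged right middle segment. It is also taken 2 h after the first dose, and sensitivity analysis 1 in SAP 7.1.5.1 asks whether drug has already lowered it. If it has, adjustment could remove part of a drug effect. Both limits stand. They apply equally to the primary ANCOVA, and Protocol 5.4 expects little or no drug effect on baseline protein. They are reasons not to call the adjusted value a pure LPS rise.

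**The dataset may hold more.** 745_PD is labelled corrected, and in the copy read here the table stops within the sex row and its footnotes are not visible. A reader might infer that no variable holds baseline-corrected protein. That cannot be established; the visible fault is ambiguity.

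**The stakes are low.** The objective is exploratory and no decision rule uses it. With placebo at zero exposure, part of any relation is a randomised contrast. This is correct and limits the weight of the point.

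**Conclusion.** The mismatch is real and can be confirmed from the text alone: a defined exploratory endpoint has no committed analysis or display, and the one sentence that could supply it is optional and unspecified. The primary analysis and the interim rules are unaffected.

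The precision at stake cannot be fixed from the documents. The 9% to 36% of variance, and the 10% to 56% equivalent in participants, rest on an assumed correlation of 0.3 to 0.6. They describe what an adjusted regression would gain over an unadjusted one, not a loss in an analysis the SAP plans. The break-even of 0.30 for the ratio rests on placeholder SDs. What does not depend on these assumptions is the case for stating one response, committing to it and labelling the variables accordingly.

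**What to change.** - **SAP 10.1:** commit to an exposure-response analysis of log 26 h LPS-lobe protein on each exposure measure already listed, with log 2 h protein as covariate, matching the primary model. Do not offer the simple 26 h/2 h ratio as an equivalent. State that the baseline is post-dose and from a different, unchallenged segment.
- **Figures 7.1 and 7.2:** show the baseline-adjusted 26 h value, for example log 26 h protein minus the fitted baseline slope times the centred log 2 h value. Keep the raw plot as a second page, which also serves as a check if the arms differ at 2 h.
- **SAP 12.9.1:** define separately the 2 h value and the 26 h LPS-lobe value for both arms, and the baseline-adjusted value. Say whether corrected means baseline or urea dilution.
- **Cross-reference:** SAP 10.1 points to Appendix 11 for the data specification; it is in Appendix 9.

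The cost is SAP wording, revised dataset labels and some extra figure pages. No new samples or assays are needed.

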12. APPENDICES

12.1. Appendix 1: Protocol Deviation Management and Definitions for Evaluable Population

12.1.1. Exclusions from Evaluable Population

Subjects with major/important protocol deviations will be excluded from Evaluable Population. The Protocol Deviation Management Plan (PDMP) will be used to determine major/important protocol deviations that will lead to exclusion from the Evaluable Population.

12.2. Appendix 2: Schedule of Activities

12.2.1. Protocol Defined Schedule of Events

- The timing and number of planned study assessments, including safety, pharmacokinetic, pharmacodynamics and exploratory biomarker assessments may be altered during the course of the study based on newly available data (e.g., to obtain data closer to the time of peak plasma concentrations) to ensure appropriate monitoring.
- Any changes in the timing or addition of time points for any planned study assessments must be documented and approved by the relevant study team member and then archived in the sponsor and site study files, but will not constitute a protocol amendment. The IRB/IEC will be informed of any safety issues that require alteration of the safety monitoring scheme or amendment of the informed consent form (ICF).

12.2.2. Screening

	Screening (Days -28 to -2)
Outpatient visit	X
Informed consent	X
Inclusion and exclusion criteria	X
Demography	X
Full physical examination	X
Height and weight	X
Medical history	X
Past and current medical conditions	X
HIV, Hepatitis B and C screening	X
FSH and oestradiol ¹	X
Drug, alcohol and cotinine screen	X
C-SSRS	X
Laboratory assessments ²	X
12-lead ECG ³	X
Vital signs ⁴	X
Spirometry ⁵	X
FOBT ⁶	X

C-SSRS: Columbia Suicide Severity Rating Scale; ECG: electrocardiogram; FOBT: Faecal Occult Blood Test; HIV: human immunodeficiency virus.

1. Postmenopausal females whose postmenopausal status is in doubt only.
2. Haematology, clinical chemistry (including liver chemistry), cardiac troponins, urinalysis and coagulation profile.
3. In triplicate.
4. Blood pressure and heart rate in triplicate. Single temperature measurement.
5. Forced expiratory volume in 1 second (FEV1) and forced vital capacity (FVC). Triplicate measurement, the highest of which should be recorded in the case report form.
6. May be measured during the screening window or on Day -1. FOBT cards will be provided at screening and must be returned to the laboratory and analysed before dosing.

12.2.3. Treatment period

	Day -1 ²	Day 1 ¹									Day 2 ¹			Day 4	
		Pre-dose	0 h	1 h	2 h	3 h	6 h	8 h	12 h	14 h	25.5 h	26 h	30 h		
Inpatient stay ²		←-----→													
Telephone call ³															X
Drug, alcohol and cotinine screen	X														
Laboratory assessments ⁴	X												X		
12-lead ECG ⁵	X	X											X		
Blood pressure and heart rate ⁵	X	X		X			X		X	X			X		
Temperature ⁶	X	X		X	X		X	X	X	X			X		
Spirometry ⁷	X	X					X				X		X		
C-SSRS													X		
Randomisation		X													
Study treatment			X						X						
Pulse oximetry ⁸					X							X			
Bronchoscopy, baseline BAL and challenge ⁹					X										
Bronchoscopy and post-challenge BAL ¹⁰												X			
Blood sample for exploratory biomarkers ¹¹					X ¹¹	X		X				X ¹¹			
Blood sample for PK		See footnote 12													
AE review		←-----→													
SAE review		←-----→													
Concomitant medication review		←-----→													

AE: adverse event; BAL: bronchoalveolar lavage; ECG: electrocardiogram; PK: pharmacokinetic; SAE: serious adverse event, C-SSRS: Columbia Suicide Severity Rating Scale.

1. Time points relative to the first dose on Day 1.
2. Admission on Day -1, at a time to allow all Day -1 procedures to be done; discharge on Day 2, at least 4 h after the bronchoscopy.
3. To check for any AEs.
4. Haematology, clinical chemistry (including liver chemistry), cardiac troponins, urinalysis and coagulation profile.
5. Triplicate on Day-1 and pre-dose. Single measurements at time points after dosing.
6. Immediately before BAL sampling/LPS challenge at the 2-h time point.
7. Forced expiratory volume in 1 second (FEV1) and forced vital capacity (FVC). Triplicate measurements at each time point, the highest of which should be recorded in the case report form.
8. Pulse oximetry to be measured during bronchoscopy procedures. Only AEs to be recorded.
9. BAL samples for total protein, neutrophil counts, GSK2798745 and exploratory biomarkers. Baseline BAL sample from a segment in the left lower lobe, followed by segmental challenge of the lungs: LPS in right middle segment; saline control in the lingula segment of the contralateral side. Challenges to be done as close as possible to 2 h post-dose.
10. BAL samples for total protein, neutrophil counts, GSK2798745 and exploratory biomarkers. Baseline and post-dose measurements to be done by the same person, where possible.
11. Blood samples for exploratory biomarkers. The 2- and 26-h blood samples should be taken immediately before BAL sampling.
12. PK samples will be taken pre-dose and at 0.5, 1, 1.5, 2, 2.5, 3, 6, 8, 12, 12.5, 13, 13.5, 14, 15, 24 and 26 h after the first dose. The 2- and 26-h blood sample should be taken immediately before BAL sampling

12.2.4. Follow-up/Early Withdrawal

	Follow-up/Early Withdrawal (Day 8 [± 1 day])
Outpatient visit	X
Full physical examination	X
Weight	X
Laboratory assessments ¹	X
12-lead ECG ²	X
Vital signs ³	X
Spirometry ⁴	X
FOBT ⁵	X
AE review	X
SAE review	X
Concomitant medication review	X

AE: adverse event; ECG: electrocardiogram; FOBT: Faecal Occult Blood Test; SAE: serious adverse event.

1. Haematology, clinical chemistry (including liver chemistry), cardiac troponins and urinalysis.
2. Single measurement.
3. Blood pressure, heart rate, temperature. Single measurement.
4. Forced expiratory volume in 1 second (FEV1) and forced vital capacity (FVC). Triplicate measurement, the highest of which should be recorded in the case report form.
5. FOBT cards will be provided upon discharge from the unit and should be returned by the follow-up/early withdrawal visit.

12.3. Appendix 3: Assessment Windows

12.3.1. Definitions of Assessment Windows for Analyses

Refer to the Study Reference Manual (SRM) for acceptable time deviation windows for study assessments and procedures.

26h PK blood samples that are taken outside of 25.5h-26.5h will be excluded from plasma concentration by time point summary tables as well as displays that include planned timepoint. The 26h blood PK sample has a wider acceptable time deviation window than other blood PK samples due to the requirement for the sample to be aligned with the 26h BAL sample. This may impact on PK summaries.

12.4. Appendix 4: Study Phases and Treatment Emergent Adverse Events

12.4.1. Study Phases

Assessments and events will be classified according to the time of occurrence relative to the two study treatment doses and LPS/saline challenges.

Study Phase	Definition
Pre-Treatment	Date/Time \leq Study Treatment Start Date/Time
Post-Treatment	Study Treatment Start Date/Time $<$ Date/Time

NOTES:

- Study Treatment Start relates to the 1st dose received by the individual.

12.4.1.1. Study Phases for Concomitant Medication

Study Phase	Definition
Prior	If medication end date is not missing and is before 28 days prior to screening visit
Concomitant	Any medication that is not a prior

NOTES:

- Please refer to [Appendix 7: Reporting Standards for Missing Data](#) for handling of missing and partial dates for concomitant medication. Use the rules in this table if concomitant medication date is completely missing.

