## 2.1. Screening

	Screening (Days -28 to -2)
Outpatient visit	X
Informed consent	X
Inclusion and exclusion criteria	X
Demography	X
Full physical examination	X
Height and weight	X
Medical history	X
Past and current medical conditions	X
HIV, Hepatitis B and C screening	X
FSH and oestradiol 	X
Drug, alcohol and cotinine screen	X
C-SSRS	X
Laboratory assessments 	X
12-lead ECG 	X
Vital signs 	X
Spirometry 	X
FOBT 	X

C-SSRS: Columbia Suicide Severity Rating Scale; ECG: electrocardiogram; FOBT: Faecal Occult Blood Test; HIV: human immunodeficiency virus.

1. Postmenopausal females whose postmenopausal status is in doubt only.
2. Haematology, clinical chemistry (including liver chemistry), cardiac troponins, urinalysis and coagulation profile.
3. In triplicate.
4. Blood pressure and heart rate in triplicate. Single temperature measurement.
5. Forced expiratory volume in 1 second (FEV1) and forced vital capacity (FVC). Triplicate measurement, the highest of which should be recorded in the case report form.
6. May be measured during the screening window or on Day -1. FOBT cards will be provided at screening and must be returned to the laboratory and analysed before dosing.

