
 
12. Use of prescription or non-prescription drugs (except paracetamol), including vitamins, herbal and dietary supplements (including St John's Wort) within 7 days or 5 half-lives (whichever is longer) before the first dose of study medication, unless, in the opinion of the investigator and GSK Medical Monitor, the medication will not interfere with the study procedures or compromise participant safety.
 
13. History of sensitivity to any of the study medications, or components thereof or a
 

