### **7.7.2. Prohibited Medications**

Except for the permitted medications noted above (Section [7.7.1](#)), participants must abstain from taking prescription or non-prescription drugs (including vitamins and dietary or herbal supplements) within 7 days (or 14 days if the drug is a potential enzyme inducer) or 5 half-lives (whichever is longer) before the start of study treatment until completion of the follow-up visit, unless, in the opinion of the investigator and sponsor, the medication will not interfere with the study.

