12.11.4. Study Population Tables

Study Population Tables					
No.	Population	IDSL / Example Shell	Title	Programming Notes	Deliverable [Priority]
Subject Disposition					
1.1.	All Subjects	ES1	Summary of Participant Disposition for the Participant Conclusion Record	ICH E3, FDAAA, EudraCT	SAC [1]
1.2.	All Subjects	SD1	Summary of Treatment Status and Reasons for Discontinuation of Study Treatment	ICH E3	SAC [1]
1.3.	Screened	ES6	Summary of Screening Status and Reasons for Screen Failure	Journal Requirements	SAC [1]
Protocol Deviation					
1.4.	All Subjects	DV1	Summary of Important Protocol Deviations	ICH E3	SAC [1]
Population Analysed					
1.5.	All Subjects	SP1	Summary of Study Populations	IDSL	SAC [1]
1.6.	All Subjects	SP2	Summary of Exclusions from the Evaluable Population	IDSL	SAC [1]
Demographic and Baseline Characteristics					
1.7.	All Subjects	DM1	Summary of Demographic Characteristics	ICH E3, FDAAA, EudraCT	SAC [1]
1.8.	All Subjects	DM11	Summary of Age Ranges	EudraCT	SAC [1]
1.9.	All Subjects	DM5	Summary of Race and Racial Combinations	ICH E3, FDA, FDAAA, EudraCT	SAC [1]
Prior and Concomitant Medications					
1.10.	All Subjects	MH1	Summary of Past Medical Conditions	ICH E3	SAC [1]

Study Population Tables					
No.	Population	IDSL / Example Shell	Title	Programming Notes	Deliverable [Priority]
1.11.	All Subjects	MH1	Summary of Current Medical Conditions	ICH E3	SAC [1]
1.12.	All Subjects	CM1	Summary of Concomitant Medications	ICH E3	SAC [1]
Exposure and Treatment Compliance					
1.13.	All Subjects	EX1	Summary of Exposure to Study Treatment	ICH E3 Exclude "Days on study drug" and "Daily Dose" from IDSL template.	SAC [1]

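### SAP 12.4.1.1 counts drugs stopped up to 30 to 56 days before the first dose as concomitant, so Table 1.12 pools them with medicines taken after dosing

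*SAP*

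**What the plan says.** SAP 12.4.1.1 sets two classes for medicines. A medicine is Prior "If medication end date is not missing and is before 28 days prior to screening visit". Concomitant is "Any medication that is not a prior". Neither class refers to dosing, and a medicine with no end date falls into Concomitant.

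The neighbouring rules use another anchor. SAP 12.4.1, immediately above, splits pre- and post-treatment at the start of treatment and notes: "Study Treatment Start relates to the 1st dose received by the individual". Protocol 6.2, exclusion 12, restricts drug use "within 7 days or 5 half-lives (whichever is longer) before the first dose of study medication". Protocol 7.7.2 sets a similar washout, with 14 days for potential enzyme inducers, and runs the restriction "before the start of study treatment until completion of the follow-up visit".

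SAP 6.1 says that the study population analyses will cover both prior and concomitant medications. Appendix 11 then lists only two medication displays: Table 1.12, "Summary of Concomitant Medications", and Listing 11, whose title is likewise limited to concomitant medications. Neither carries a note that separates use before dosing from use after it.

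**The concern.** A reader of the clinical study report will take a table of concomitant medications to show what participants took while they were on study. Protocol 7.7.1 allows paracetamol, salbutamol, midazolam and other drugs case by case, so there is real on-study use to describe. Under the SAP rule the same table also counts drugs that ended weeks before the first dose, some of them stopped precisely because the protocol required it.

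Two things follow. First, with at most 30 evaluable participants per arm, a few courses that ended before dosing could blur or mimic a difference between arms in on-study use. Second, the boundary depends on when a participant happened to be screened, which has nothing to do with exposure to study drug or LPS.

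**Working it through.** The plan gives no figure to reproduce, so the check is date arithmetic.

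**Inputs**
- Cut-off: 28 days before the screening visit (SAP 12.4.1.1).
- Screening: Day -28 to Day -2 (Protocol 2.1).
- Study-day rule: for dates before the first dose, study day = date minus first-dose date (SAP 12.6.1). Day -28 and Day -2 are therefore 28 and 2 days before dosing.
- Washout: 7 days, 14 days for a potential enzyme inducer, or 5 half-lives if longer (Protocol 6.2 and 7.7.2).

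**Cut-off in days before the first dose** = (days from screening to first dose) + 28
- Screened on Day -28: 28 + 28 = 56.
- Screened on Day -2: 2 + 28 = 30.
- Spread between participants: 56 - 30 = 26 days.

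**Washed-out drugs still labelled Concomitant** (for drugs whose 5 half-lives do not exceed the fixed period)
- 7-day washout: ended 8 to 56 days before dosing if screened on Day -28 (56 - 7 = 49 days), or 8 to 30 days if screened on Day -2 (30 - 7 = 23 days).
- 14-day washout: ended 15 to 56 days before dosing (56 - 14 = 42 days), or 15 to 30 days (30 - 14 = 16 days).

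**Test end dates under the SAP rule and under a first-dose rule**

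| Drug ended (days before first dose) | SAP rule, screened Day -28 | SAP rule, screened Day -2 | First-dose rule |
|---|---|---|---|
| 57 | Prior | Prior | Prior |
| 56 | Concomitant | Prior | Prior |
| 40 | Concomitant | Prior | Prior |
| 30 | Concomitant | Concomitant | Prior |
| 8 | Concomitant | Concomitant | Prior |
| 1 | Concomitant | Concomitant | Prior |
| 0 (dosing day) or later | Concomitant | Concomitant | Concomitant |
| End date missing | Concomitant | Concomitant | Concomitant |

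The 40-day row shows the dependence on screening date: one drug history, two labels. The date conventions do not offset this. SAP 12.7.2.1 imputes a partial stop date to the end of the month, and to December if the month is missing, which can only move more drugs into Concomitant.

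**The case against.** The best defence is that 12.4.1 concerns assessments and events, while 12.4.1.1 is a separate rule written for medicines. A generous look-back is a convention, and it keeps recent pre-dose use in the summary. That explains why the two sections can differ. It does not explain a boundary that shifts with screening date, or why a class called Concomitant should hold drugs that ended before dosing. Its useful part, keeping recent pre-dose use in a summary, should survive in the fix.

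Three stronger readings are tempting, and the documents do not support them.

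- A reader might infer that Table 1.12 fails to show on-study medicines. It does show them, because everything that is not Prior is included. They are pooled, not lost.
- A reader might infer that washout compliance cannot be assessed. SAP 4.1 provides for important protocol deviations to be summarised and listed, with a separate summary and listing of eligibility deviations (Table 1.4, Listings 6 and 7). Under SAP 12.1.1, major or important deviations lead to exclusion from the Evaluable population. Compliance is handled there.
- A reader might compare the 30 to 56 days before dosing with the week or so after it and infer that most of the table's content predates dosing. That is a ratio of calendar days. It would hold for medicines only if use were even over time, which does not fit washout rules in healthy volunteers or drugs tied to bronchoscopy and spirometry.

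Two further points stand. Listing 11 may allow a manual split, since SAP 12.7.2.1 has recorded partial dates displayed in listings; its layout is not in the text. And a first-dose boundary does not isolate medicines that could have influenced the 26 h lavage. Day 8 is 7 days, or 168 h, after the first dose, so 142 of those 168 h (about 85%) come after that sample. The fix gives a correct description of on-study use, not an analysis of what affected the endpoint.

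**Conclusion.** The point holds as a minor error in descriptive reporting. The rule labels as Concomitant any drug that ended up to 30 to 56 days before the first dose, including drugs properly washed out. Table 1.12 cannot separate these from medicines taken after dosing, and identical histories can be classed differently by screening date alone.

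The size is known in days, not in records. It depends on how far back the case report form records medicines, which the documents do not settle: the screening schedule has no concomitant medication row, and the start of the review arrow in the treatment-period schedule cannot be read reliably. The existence of a Prior class implies that earlier drugs can be recorded.

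No model, interim decision or analysis population uses this classification, so the primary analysis is unaffected.

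**What to change.** In SAP 12.4.1.1, replace the screening-based rule with the following.

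- Prior: known end date before the first-dose date.
- Concomitant: taken on or after the first-dose date, that is, ongoing at that date, started on or after it, or with a missing end date.

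Present the two classes as separate blocks of Table 1.12, or as two tables, which also delivers the prior and concomitant analyses that SAP 6.1 promises. Add the class as a flag in Listing 11. Prior medicines should not be moved to the listing alone: a drug stopped a day or two before dosing, inside the washout period, would then vanish from the only medication summary.

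The cost is one extra derivation and one extra table block. SAP 12.7.2.1 already handles medication start and stop dates, so no new data are needed. The change concerns how medicines are reported and leaves the protocol's medication rules as they are.
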